10.2 Study population

The study population will consist of all patients who are registered and receive at least one dose of axitinib. All efficacy and safety analyses will be conducted using the study population. Any patient who is registered on to this trial but never receives study treatment will be described, including the reason(s) for non-participation.

10.3 Statistical Analysis

Data analysis will primarily be descriptive in nature, although as discussed above the underlying hypothesis that axitinib titration can improve PFS will be tested using a MLE test. Categorical data, such as adverse events and response rate, will be summarized using proportions and frequencies. Continuous endpoints, such as dose information will be summarized using medians and ranges, and PFS and overall survival will be summarized using the Kaplan-Meier method.

11. ETHICS

11.1 Informed Consent

Subject / Legally acceptable representative (LAR) (as applicable) consent must be obtained according to institutional review board (IRB) and/or ethics committee (EC) requirements prior to any study-specific screening procedures. Sample English consent forms for the trial will

be provided. A copy of the initial IRB/EC full board approval and approved consent form must be sent to Cleveland Clinic. The subject/LAR must sign consent prior to registration.

11.2 Institutional Review Board Approval

Initial approval: Full approval of the protocol and consent form by the appropriate IRB/EC must be obtained prior to commencement of the clinical trial.

Continuing approval: Annual (or as required by the IRB/EC re-approval may be required for as long as subjects are being followed on protocol. It will be investigator's responsibility to apply for and obtain the re-approval.

Amendment: All protocol amendments will be confirmed in writing and submitted, as appropriate, for review by the IRB/EC and health authorities. Amendments will be reviewed and approved by applicable regulatory authorities prior to central implementation of the amendment, and by IRB/ECs prior to local implementation, EXCEPT when the amendment eliminates an immediate hazard to clinical trial subjects or when the change(s) involves only logistical or administrative aspects of the trial.

Serious Adverse Events, Safety Updates and Investigator Brochure Updates: During the course of the study serious adverse events, safety updates or investigator brochure updates may be sent to you for reporting to your IRB/EC. If/when this occurs documentation of IRB/EC submission of this information must be forwarded to Cleveland Clinic.

12. DOCUMENTATION, RECORD ACCESS AND MAINTENANCE OF STUDY RECORDS

12.1 Documentation of subject's participation

A statement acknowledging the participation of a subject in this clinical trial must be documented in the subject's medical records.

12.2 Regulatory Requirements

The following are required from all investigators:

- Completion of CITI - Collaborative Institutional Training Initiative
- Completion of necessary IRB/EC training.

12.3 Subject Confidentiality

Any research information obtained about the subject in this study will be kept confidential. A subject will not be identified by name, only by his/her initials. The subject's name or any identifying information will not appear in any reports published as a result of this study.

However, information obtained from individual subject's participation in the study may be disclosed with his/her consent to the health care providers for the purpose of obtaining appropriate medical care. The subject's medical records/charts, tests will be made available to Pfizer, the Cleveland Clinic Taussig Cancer Institute, the IRB, and any other regulatory authorities. This is for the purpose of verifying information obtained for this study. Confidentiality will be maintained throughout the study within the limits of the law.

A subject's name will not be given to anyone except the researchers conducting the study, who have pledged an oath of confidentiality. All identifying information will be kept behind locked doors, under the supervision of the study Principal Investigator and will not be transferred outside of the hospital. A subject may take away his/her permission to collect, use and share information about him/her at any time. If this situation occurs, the subject will not be able to remain in the study. No new information that identifies the subject will be gathered after that date. However, the information about the subject that has already been gathered and transferred may still be used and given to others as described above in order to preserve the scientific integrity and quality of the study.

12.4 Confidentiality of the study

Data generated as a result of this study are to be available for inspection on request by local health authority auditors, the Sponsor's Study Monitors and other personnel (as appropriate) and by the IRB. The Investigator shall permit sponsor, authorized agents of the sponsor, CRO and regulatory agency employees to enter and inspect any site where the drug or records pertaining to the drug are held, and to inspect all source documents. The protocol and other study documents contain confidential information and should not be shared or distributed without the prior written permission of sponsor.

12.5 Registration of Clinical Trial

Prior to the first subject being registered/enrolled into this study, the Sponsor will be responsible for ensuring that the clinical trial is registered appropriately to remain eligible

for publication in any major peer-reviewed journal, adhering to the guidelines put forth by the International Committee of Medical Journal Editors (ICMJE).

12.6 Data reporting

The data will be collected on eCRFs in Overture and analyzed after entry into a study database.

12.7 Case Report Forms

The eCRFs for the study will be provided by Database Manager for Cleveland Clinic .

12.8 Maintenance of study records

To enable evaluations and/or audits from Regulatory Authorities, the Sponsor, and the Investigator agrees to keep records, including the identity of all participating subjects (sufficient information to link records, CRFs and hospital records), all original signed informed consent forms, copies of all CRFs, source documents, and detailed records of treatment disposition. The Investigator should retain these records after study close-out as required by United States regulations or as specified in the Clinical Trial Agreement, whichever is longer.

If the investigator relocates, retires, or for any reason withdraws from the study, then the Sponsor should be prospectively notified. The study records must be transferred to an acceptable designee, such as another investigator, another institution, or to the Sponsor. The investigator must obtain the Sponsor's written permission before disposing of any records.

13. QUALITY ASSURANCE AND QUALITY CONTROL

As per the Guidelines of Good Clinical Practice (CPMP/ICH/135/95), the sponsor will be responsible for implementing and maintaining quality assurance and quality control systems.

13.1 On site Monitoring / Auditing

13.1 Audits and inspections

Authorized representatives of the sponsor, a regulatory authority, an Independent Ethics Committee (IEC) or an Institutional Review Board (IRB) may visit the Center to perform audits or inspections, including source data verification. The purpose of an audit or inspection is to systematically and independently examine all study-related activities and documents to determine whether these activities were conducted, and data were recorded,

analysed, and accurately reported according to the protocol, Good Clinical Practice (GCP), guidelines of the International Conference on Harmonization (ICH), and any applicable regulatory requirements.

13.2 Data Safety and Monitoring Plan

This protocol will adhere to the policies of the Case Comprehensive Cancer Center Data and Safety Monitoring Plan in accordance with NCI regulations.

14. ADMINISTRATIVE PROCEDURES

14.1 Amendments to the protocol

Modifications of the signed protocol are only possible by approved protocol amendments authorized by the Sponsor. All protocol amendments will be approved by the IRB prior to implementation. The Investigator must not implement any deviation from, or change to the protocol, except where it is necessary to eliminate an immediate hazard to trial subject or when the change(s) involves only logistical or administrative aspects of the trial.

14.2 Protocol deviations and Violations

All violations or deviations are to be reported to the site's IRB. All IRB correspondence is to be forwarded to Cleveland Clinic. The site must notify Cleveland Clinic immediately of any protocol violations.

14.3 Premature discontinuation of the study

The Sponsor reserves the right to discontinue the trial for any reason but intends only to exercise this right for valid scientific or administrative reasons. After such a decision, the Investigators must contact all participating patients immediately after notification. Standard therapy and follow-up for subjects will be assured and, where required by the applicable regulatory requirement(s), the relevant regulatory authority(ies) will be informed.

The IRB will be informed promptly and provided with a detailed written explanation for the termination or suspension.

As directed by the Sponsor, all study materials must be collected and all CRFs completed to the greatest extent possible.

15. APPENDICES

15.1 RECIST 1.1 Criteria

The determination of antitumor efficacy during this study will be based on objective tumor assessments made according to the RECIST system of unidimensional evaluation.

Measurability of Tumor Lesions

At baseline, individual tumor lesions will be categorized by the investigator as either measurable or non-measurable by the RECIST criteria as described below.

Measurable:

Tumor lesion: Must be accurately measured in at least one dimension (longest diameter in the plane of measurement is to be recorded) with a minimum size of:

- 10 mm by CT scan (CT scan slice thickness no greater than 5 mm);
- 10 mm caliper measurement by clinical exam (lesions which cannot be accurately measured with calipers should be recorded as non-measurable).

Malignant lymph nodes: To be considered pathologically enlarged and measurable, a lymph node must be ≥ 15 mm in short axis when assessed by CT scan (CT scan slice thickness recommended to be no greater than 5 mm). At baseline and in follow-up, only the short axis will be measured and followed.

Non-Measurable: All other lesions, including small lesions (longest diameter < 10 mm or pathological lymph nodes with ≥ 10 mm to < 15 mm short axis) as well as truly non-measurable lesions. Lesions considered truly non-measurable include: leptomeningeal disease, ascites, pleural or pericardial effusion, inflammatory breast disease, lymphangitic involvement of skin or lung, abdominal masses/abdominal organomegaly identified by physical exam that is not measurable by reproducible imaging techniques.

NOTE: If measurable disease is restricted to a solitary lesion, its neoplastic nature should be confirmed by cytology/histology.

Recording Tumor Measurements

All measurable lesions up to a maximum of 2 lesions per organ and 5 lesions in total representative of all involved organs should be identified as **target lesions** and measured and recorded at baseline and at the stipulated intervals during treatment. Target lesions should be selected on the basis of their size (lesion with the longest diameters) and their suitability for accurate repetitive measurements (either by imaging techniques or clinically).

The longest diameter will be recorded for each target lesion. The sum of the longest diameter for all target lesions will be calculated and recorded as the baseline sum longest

diameter to be used as reference to further characterize the objective tumor response of the measurable dimension of the disease during treatment. All measurements should be performed using a caliper or ruler and should be recorded in metric notation in centimeters.

All other lesions (or sites of disease) should be identified as **non-target lesions** and should also be recorded at baseline. Measurements are not required and these lesions should be followed as "present" or "absent."

Techniques for Assessing Measurable Disease

The same method of assessment and the same technique should be used to characterize each identified and reported lesion at screening and during follow-up. Imaging-based evaluation is preferred to evaluation by clinical (physical) examination when both methods have been used to assess the antitumor effect of a treatment.

Definitions of Tumor Response

Target Lesions

Complete response (CR) is defined as the disappearance of all target lesions. Any pathological lymph nodes (whether target or non-target) must have reduction in short axis to <10 mm.

Partial response (PR) is defined as a $\geq 30\%$ decrease in the sum of the longest dimensions of the target lesions taking as a reference the baseline sum longest dimensions.

Progressive disease (PD) is defined as a $\geq 20\%$ increase in the sum of the longest dimensions of the target lesions taking as a reference the smallest sum of the longest dimensions recorded since the treatment started, or the appearance of one or more new lesions. In addition to the relative increase of 20%, the sum must also demonstrate an absolute increase of at least 5 mm.

Stable disease (SD) is defined as neither sufficient shrinkage to qualify for PR nor sufficient increase to qualify for PD taking as a reference the smallest sum of the longest dimensions since the treatment started.

Non-Target Lesions

Complete response (CR) is defined as the disappearance of all non-target lesions. All lymph nodes must be non-pathological in size (<10 mm short axis).

Non-CR/Non-PD is defined as a persistence of ≥ 1 non-target lesions.

Progressive disease (PD) is defined as unequivocal progression of existing non-target lesions, or the appearance of ≥ 1 new lesion.

The cytological confirmation of the neoplastic origin of any effusion that appears or worsens during treatment when the measurable tumor has met criteria for response or stable disease is mandatory to differentiate between response or stable disease and progressive disease.

Confirmation of Tumor Response

To be assigned a status of PR or CR, changes in tumor measurements in patients with responding tumors must be confirmed by repeat studies that should be performed ≥ 4 weeks after the criteria for response are first met. In the case of SD, follow-up measurements must have met the SD criteria at least once after study entry at a minimum interval of 8 weeks.

Determination of Tumor Response by the RECIST Criteria

When both target and non-target lesions are present, individual assessments will be recorded separately. Determination of tumor response at each assessment is summarized in the following table.

Response Evaluation Criteria in Solid Tumors

Target Lesions¹	Non-Target Lesions²	New Lesions³	Tumor Response
CR	CR	No	CR
CR	Non-CR/non-PD	No	PR
CR	Not evaluated	No	PR
PR	Non-PD or not all evaluated	No	PR
SD	Non-PD or not all evaluated	No	SD
PD	Any response	Yes or No	PD
Any response	PD	Yes or No	PD
Any response	Any response	Yes	PD

¹ Measurable lesions only.

² May include measurable lesions not followed as target lesions or non-measurable lesions.

³ Measurable or non-measurable lesions.

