Test Drug Administration:	
The intent is to maximize dose intensity of axitinib based on individual tolerability using the dose modification criteria described in Section 5. Dose changes are done if selected toxicity (oral mucositis, diarrhea, fatigue, hand-foot syndrome) is \leq grade-2. There will be no mandated dosing or schedule changes for hypertension, hypothyroidism, skin color changes, heartburn etc. Patients will continue therapy until progression according to RECIST criteria version 1.1 or investigator discretion of clinical benefit. Patients may undergo dose escalation following disease progression at the discretion of the provider.

Treatment and Post-Treatment Assessments:	
One cycle is defined as 28 days.
 
During the first cycle:
 
 • History and Physical exam at beginning of each cycle • CBC with differential • Complete Metabolic Panel (CMP) • Thyroid function tests • Telephone encounter during first week to assess toxicity • Phone call after two weeks to assess toxicity 
During Subsequent Cycles:
 
 • History and Physical exam at beginning of each cycle • CBC with differential at beginning of each cycle • CMP at beginning of each cycle • Telephone call or clinic visit 7 & 14 days after each dose change • Clinic visits or telephone calls as needed to assess toxicity 
Every two cycles:
 
 • Restaging of involved areas • Thyroid function tests
Response:	Response will be assessed as per RECIST version 1.1
Safety Variables & Analysis:	Adverse Events will be assessed as per CTCAE version 4.03

ABBREVIATIONS

ADL	Activities of Daily Living
ADR	Adverse Drug Reaction
AE	Adverse Events
AHFS	American Hospital Formulary Service
ANC	Absolute Neutrophil Count
ASHP	American Society of Hospital Pharmacists
AUC	Area Under the Curve
BID	Twice Daily
BP	Blood Pressure
CBC	Complete Blood Count
CCCC	Case Comprehensive Cancer Center
CCF	Cleveland Clinic Foundation
CITI	Collaborative Institutional Training Initiative
C_{\max}	Maximum Plasma Concentration
CMP	Comprehensive Metabolic Panel
CNS	Central Nervous System
CR	Complete Response
CRF	Case Report Form
CRO	Contract Research Organization
CTCAE	Common Terminology Criteria for Adverse Events
DCRU	Dahm's Clinical Research Unit
DSTC	Data Safety and Toxicity Committee
EC	Ethics Committee
EKG	Electrocardiogram
FDA	Food and Drug Administration
HR	Hazard Ratio

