4. STUDY CALENDAR

Required Investigations	Baseline (within 4 weeks prior to C1D1)	First Cycle (28 days)		Day 7 and 14 after each dose change (+/- 2 working days)	Each Cycle Day 1^{3,5} (28 days +/- 3 working days)	Safety assessment⁶ (Within 30 days after off treatment +/- 3 days)
		Day 7¹ (+/- 2 working days)	Day 14¹ (+/- 2 working days)			
History and Physical Exam	X				X ⁹	
KPS and ECOG performance status	X				X	
Informed consent	X					
Assessment of Toxicity		X (phone call)	X (phone call)	X (phone call and/or clinic visit)	X	Assess for resolution of treatment-related toxicities within 30 days of last dose
CBC w/ differential, CMP, and LDH⁷	X				X	as clinically indicated
TSH, T3, T4	X				X ⁴	as clinically indicated
Pregnancy Test⁸	X					
EKG	X					
Radiographic Assessment²	X				X ⁵	
Patient diary (BP/dosing)	X-----X					

1 No dose escalation prior to day 14 of cycle 1

2 CTs (head, chest, abdomen, pelvis; with oral and IV contrast if possible) and bone scan required at baseline and must be done within 28 days of registration. MRI is allowed instead of CT head at baseline.. CT head will be done after baseline as clinically indicated. Follow-up scans are based on C1D1 date regardless of the date of baseline scans.

3 Beginning at C5D1 this column can be extended to every 2 cycles per provider discretion. Following C13D1 visit, this can be extended to every 12 weeks (i.e., 3 cycles)

4 Tests to be done at imaging timepoints

5 After baseline, bone scan only if indicative of metastatic disease at baseline or if clinical signs/symptoms develop. CT Chest-Abdomen-Pelvis will be done every 8 weeks based on C1D1 date regardless of the date of baseline scans. Following Cycle 13 Day 1 assessment, CT scans to be done every 12 weeks. [Note: patients continuing axitinib post-PD will have CT c/a/p every 8 weeks and bone scans as needed per MD discretion]

Following Cycle 7 Day 1 disease assessment, bone scan to be done every 16 weeks per MD discretion (and every 24 weeks after C13 per MD discretion)

6 Treatment-related AE reporting ends at the time new treatment is started (see section 9.6). After C13D1, all SAEs will be documented, AEs will be followed per SOC but not necessary to document for study-related purposes.

7 LDH at baseline only

8 Serum pregnancy test for women of childbearing potential. No childbearing potential defined as > 12 months of non-therapy-induced amenorrhea or surgically sterile.

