9 Targeted physical exam per MD discretion when patient is in for a clinic visit
 Protocol treatment should begin within 3 working days of patient registration.

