8.2 Efficacy assessments

Patients must have measurable disease at screening and will be evaluated for response on the basis of RECIST criteria version 1.1 (Section 15.1). Tumor measurements using physical examination, spiral CT scan and/or MRI or other appropriate techniques deemed suitable by the investigator will be performed at screening within 28 days of patient registration and repeated every 8 weeks until disease progression. After baseline, bone scan only if indicative of metastatic disease at baseline or if clinical signs/symptoms develop. CT Chest-Abdomen-Pelvis will be done every 8 weeks based on C1D1 date regardless of the date of baseline scans. Following Cycle 13 Day 1 assessment, CT scans to be done every 12 weeks. Disease assessment with CT chest-abdomen-pelvis will continue every 8 weeks for patients continuing on treatment following disease progression (bone scans to be done per MD discretion). Scans can be done more frequently per MD discretion; these scans will be submitted on an unscheduled disease assessment CRF.

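### The 8-week minimum for stable disease leaves no room for the calendar's scan window, so a compliant first CT can fail to count as SD

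*Combined protocol and SAP*

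**What the plan says.** Section 15.1 (Confirmation of Tumor Response) requires that, for SD, "follow-up measurements must have met the SD criteria at least once after study entry at a minimum interval of 8 weeks". It gives no tolerance and does not say whether study entry means registration, C1D1 or the baseline scan.

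The scan schedule is in two places. Study Calendar footnote 5 says "CT Chest-Abdomen-Pelvis will be done every 8 weeks based on C1D1 date regardless of the date of baseline scans", and section 8.2 says tumor measurements are "repeated every 8 weeks until disease progression". The Synopsis fixes the cycle length: "One cycle is defined as 28 days". The Radiographic Assessment row is marked in the calendar column for Day 1 of each cycle, whose header carries the window "28 days +/- 3 working days". Neither footnote 5 nor section 8.2 states a separate window for CT.

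Two further passages bear on the anchor. The calendar notes say "Protocol treatment should begin within 3 working days of patient registration", and section 8.2 says baseline measurements "will be performed at screening within 28 days of patient registration".

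Section 10.1 lists RECIST-based response among the secondary endpoints, and section 10.3 summarizes response rate by proportions and frequencies.

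**The concern.** The minimum interval for SD and the due date of the first scan are the same number, and the window lets the scan come earlier. A site that follows the calendar can thus produce a first scan that the SD rule does not accept. If that patient has progressed by the week-16 scan, or has no later scan, no assessment satisfies the SD rule. The patient's category then turns on which day the scan was booked rather than on the course of the disease. Because the anchor is undefined, two sites could also treat identical patients differently.

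What is at stake is the breakdown of RECIST-based response into SD and PD or not evaluable. The rule plays no part in the definition of PFS or in the count of complete and partial responses.

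**Working it through.** **Inputs.** SD minimum: 8 weeks (15.1). First CT: 8 weeks from C1D1 (calendar footnote 5; section 8.2). Cycle: 28 days (Synopsis). Window: plus or minus 3 working days (calendar column header). Registration to first dose: 0 to 3 working days (calendar notes). Baseline scan: up to 28 days before registration (8.2). Median PFS 6.5 and 9.5 months, exponential, N = 38 (10.1).

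**Step 1: the plan's own dates.** The first CT is due after 2 × 28 = 56 days, and the SD minimum is 8 × 7 = 56 days. The slack is 56 − 56 = 0 days.

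**Step 2: C1D1 as the anchor.** Days from C1D1 to a first scan taken early but inside the window:

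| C1D1 weekday | 1 working day early | 2 early | 3 early |
|---|---|---|---|
| Mon | 53 | 52 | 51 |
| Tue | 55 | 52 | 51 |
| Wed | 55 | 54 | 51 |
| Thu | 55 | 54 | 53 |
| Fri | 55 | 54 | 53 |

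Every entry is below 56. A scan on the due date or later qualifies.

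**Step 3: registration as the anchor.** Registration precedes C1D1 by 0 to 3 working days, or 0 to 5 calendar days. Adding this lag to the due-date and early-scan days gives intervals from 51 to 61 days. For each weekday, 3 early-scan days × 4 lags = 12 combinations, of which 6 are below 56. Monday, for example, has scan days 53, 52, 51 and lags 0, 3, 4, 5; the sums below 56 are 53, 52, 55, 51, 54 and 55. These are counts of combinations, not probabilities.

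**Step 4: baseline scan as the anchor.** The worst shortfall is 56 − 51 = 5 days, so failure requires a baseline scan fewer than 5 days before C1D1. That is permitted, but it is only a small part of the 28 days allowed.

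**Step 5: how many patients could depend on the first scan.** Under the plan's exponential model, with 30.4375 days per month, the share with a PFS event between days 56 and 112 is S(56) − S(112), where S(t) = exp(−ln 2 × t / median).

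- Median 6.5 months: 0.822 − 0.675 = 0.146 (from unrounded values); × 38 = 5.6 patients.
- Median 9.5 months: 0.874 − 0.765 = 0.110; × 38 = 4.2 patients.

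Starting the interval at day 51 instead gives 0.161 (6.1 patients) and 0.120 (4.6 patients), so about 4 to 6 holds either way.

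**Step 6: from ceiling to affected.** Only those scanned early count. If a fraction f are, the number is at most f × (4.2 to 5.6): 0 at f = 0, 1.0 to 1.4 at f = 0.25, 2.1 to 2.8 at f = 0.5, and 4.2 to 5.6 at f = 1. The documents give no value for f.

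**The case against.** The best defense has four parts.

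**The window may not govern CT.** It is stated in a column header, while footnote 5 and section 8.2 schedule CT from C1D1 with no tolerance. However, the radiographic row sits in that column and no other window is given, so applying it to CT is the natural reading.

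**The anchor may not be C1D1.** An earlier anchor lengthens the interval. This stands in part: failures become less frequent, but steps 3 and 4 show that they remain possible under each reading.

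**Later or extra scans may rescue the patient.** A patient still in SD at week 16 does qualify. Section 8.2 adds "Scans can be done more frequently per MD discretion", but that is discretionary and so is no safeguard.

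**The consequence is small and partly inferred.** This stands, and three stronger readings should be resisted.

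- A reader might infer that such patients would be recorded as PD or not evaluable. The plan does not say so. It has no algorithm for best overall response, and the table in 15.1 assigns SD at each assessment without any minimum interval.
- A reader might infer that a named SD-rate or best-response endpoint is distorted. The secondary objective is objective response rate, section 10.1 says only RECIST-based response, and no disease-control endpoint is listed. Best observed response appears only in the heading of a table about another trial.
- A reader might take half of first scans to be early and report 2 to 3 misclassified patients. Nothing in the documents supports one half. It would also be applied to a ceiling that includes deaths and patients not in SD at the first scan.

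**Conclusion.** The inconsistency is real but minor. Followed as written, the calendar permits a first CT on days 51 to 55 that the SD rule rejects when counted from C1D1. It can also reject one counted from registration or the baseline scan, though less often. The effect is confined to patients whose only SD assessment is that scan: between 0 and about 4 to 6 of 38.

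That ceiling rests on the plan's exponential PFS at medians of 9.5 and 6.5 months, and on the column window applying to CT. It is an expected count of PFS events. Patients who leave without an event before the week-16 scan are not in it, and the documents give no rate for them.

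No hypothesis test or stopping guideline in the plan uses the split between SD and PD or not evaluable. The defect is a pre-specified category rule that misfires under compliant conduct and would have to be interpreted after the data are in.

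**What to change.** In section 15.1, name C1D1 as the anchor in place of study entry, and set the SD minimum at 8 weeks less the permitted calendar window. From C1D1 the earliest in-window scan is day 51, so the minimum must be no more than 51 days. Seven weeks (49 days) is convenient and leaves 51 − 49 = 2 days to spare, for example for a public holiday that stretches the working-day count. C1D1 is already the scan anchor in footnote 5 and matches the start of PFS in section 10.1 (first receipt of axitinib). One added sentence could say how a patient whose SD misses the minimum is recorded.

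An alternative is to keep 8 weeks and remove the minus side of the window for the first CT. That preserves the threshold but constrains scheduling, and a scan taken a day early would still not count.

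The cost of the preferred change is one phrase, with no added scans or visits and no change to the sample size. The downside is a slightly shorter minimum duration for SD. It should be settled before response categories are tabulated.
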